First, we will analyze if ER α -p53 interaction in tumors affects p53's function as a transcriptional regulator. Toward this goal, we will analyze a selected group of p53-target genes (based on their reported importance in regulating cell cycle and apoptosis (63,64) that are either activated or repressed by p53 in the resected tumor tissue. . ***We have already demonstrated that Survivin (whose transcription is known to be repressed by p53) expression is upregulated as a consequence of ER binding to p53, and treatment with TAM leads to functional activation of p53, thereby restoring p53's ability to repress Survivin expression (65).*** The mRNA levels of these genes will be analyzed by qRT-PCR, a technique routinely used in the PI's laboratory. Subsequently, we will analyze the expression of these genes at the protein level. Immunohistochemistry (IHC) studies of these proteins will be conducted in the core biopsy samples (unstained slides will be requested for biopsies performed outside RPCI) and surgically excised tumor tissue of the study subjects using a tissue microarray (TMA) generated by the Department of Pathology under the supervision of [name]. For patients recruited at the University of Chicago, TMA will be generated at the University of Chicago. IHC will be performed under the direction of the pathologist, with all pathology personnel blinded to treatment assignment. The IHC endpoints will be rounded to the nearest 10% by the pathologist who will be blinded to the treatment group assignment. The ER and p53 status will be determined as described in the earlier section (section 4.1.1). Staining for p21, Bax, puma and Survivin will be evaluated qualitatively and scored on a 0 – 3+ intensity scale (0 = negative staining, 1+ = weak staining, 2+ = moderately intense staining, and 3 + = strong staining. It is to be noted that p53-target gene protein expression will be analyzed by IHC both in the core biopsy samples and surgically excised tumor tissue enabling within-patient comparison of expression profile of these proteins *before* and *after* TAM therapy. Ideally, a similar within-patient approach is desirable for other assays (ChIP and qRT-PCR,) as well. However, it is practically impossible given the limited tissue availability from the pre-surgical biopsy.

VI. STATISTICAL CONSIDERATIONS

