The bio-statistician at RPCI will perform the statistical analyses and aid in interpretation of results. Exploratory graphical analysis and data confirmation will precede formal inferential analysis. As this is an investigational study, no correction for multiple testing will be made; p-values less than $\alpha=0.05$ will be deemed statistically significant. While formal power computations are provided, it is expected a larger Phase III trial will be planned to confirm and elaborate promising findings. The demographic and baseline data will be summarized by treatment group. Descriptive statistics such as frequencies and relative frequencies will be computed for all categorical variables. Numeric variables will be summarized using simple descriptive statistics such as mean, standard deviation, quartiles, etc. Ninety-five percent confidence intervals will be computed when appropriate. A variety of graphical techniques will be used to display data.

The primary analyses in Aim 1 are comparisons of ER α -p53 interaction (positive or negative) between independent treatment and control groups. The proportions of patients with positive ChIP assay/PLA will be compared with Fisher's Exact Test, which has 80% power to detect a difference of about 0.41 between the two group; e.g., a difference of 70% in the control group vs. 30% in the TAM group. In Aim 2, mean mRNA levels, as measured by qRT-PCR, will be compared across treatment and control groups. The difference in log fold intensity between treatment and control will be estimated with an independent samples t-confidence interval. The corresponding hypothesis test has

80% power to detect an effect size of 0.91. That is, if the true difference in means is about 0.91 standard deviations, there is an 80% probability our study will correctly reject the null hypothesis of no effect.

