Protein expression measured by IHC gives an ordinal variable (0, 1+, 2+, 3+). For each protein, the four-week intensity change ("post – pre" will be between -3 and 3) will be compared between treatment and control groups with the Wilcoxon-Mann-Whitney test. In the control group we expect little change because no treatment has been given between samples. For power calculations we assume 80% of patients in control will have no change and 10% will increase and decrease. As a hypothesis, we estimate half of patients in the treatment group will have no change and the rest will increase one (e.g. from 1+ to 2+) or two categories (e.g. from 1+ to 3+). From simulation we estimate the power to correctly reject the null hypothesis when this alternative is true is about 90%.

It is possible the response variables in Aims 1 and 2 are correlated with clinical factors such as patient age, smoking status, and position in menstrual cycle. Additional exploratory comparisons of response between treatment and control groups will be made after adjustment for clinical factors with linear or logistic regression as appropriate. These secondary analyses may have greater ability to detect a treatment difference by controlling variability unrelated to treatment. PK/PD data modeling was described previously. Pharmacogenomic data will be explored with the general linear model $Y = a + bG + e$, where genotype G is quantified 0, 1, 2 for aa , Aa , AA , respectively; for quantitative response Y , normal linear regression is used; for binary response, logistic regression is used.

Randomization:

Patients will be allocated to treatment or control by block randomization (block size=4). The randomization assignment list will be maintained at RPCI. The nurse/coordinator from University of Chicago will notify the RPCI Network office for a randomization assignment by sending the completed patient registration form to [contact]. The Network Monitor or designee will randomize the patient and send the randomization assignment to the nurse/coordinator at University of Chicago.

Management of Patients After Completion of Tamoxifen Treatment:

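### Each IHC marker is analysed as a raw change on a bounded 0 to 3+ score; modelling the post-treatment score with baseline category as covariate would gain a few points of power, and the 90% figure should be restated with the bounds applied

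*Combined protocol and SAP*

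**What the plan says.** Section VI (Statistical Considerations) treats IHC protein expression as a four-level ordinal score, 0 to 3+. For each protein, the four-week change (post minus pre, so between -3 and 3) "will be compared between treatment and control groups with the Wilcoxon-Mann-Whitney test".

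For the power calculation in controls, "we assume 80% of patients in control will have no change and 10% will increase and decrease". For tamoxifen, "half of patients in the treatment group will have no change and the rest will increase one" or two categories. The result is "From simulation we estimate the power to correctly reject the null hypothesis when this alternative is true is about 90" per cent. The plan does not give the split between one-step and two-step rises, the number per arm behind this figure, or any distribution of baseline scores.

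Section V (Analysis of p53-target gene transcription) says p21, Bax, puma and Survivin will be scored on both the core biopsy and the resected tumour. It gives within-patient comparison as the reason, and says limited biopsy tissue rules this out for ChIP and qRT-PCR.

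Section VI also plans exploratory adjusted comparisons and notes that they may be more sensitive. The factors it names are age, smoking and menstrual-cycle position, not the baseline IHC score.

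**The concern.** A tumour at 3+ cannot rise, and one at 2+ can rise only one step. The change score gives a capped 3+ tumour the same value, zero, as a tumour that had room to respond and did not. The baseline score tells these two apart, but the planned test uses it only through subtraction. For Survivin, which Section V describes as repressed by p53, the expected direction is a fall. The bound that matters there is 0, and the rise-only power scenario applies with its sign reversed.

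The stakes are power and interpretation, not bias. IHC is the trial's only before-and-after assay of p53-target expression, and Section VI expects a larger trial to follow promising findings. If the 90% makes no allowance for the bounds, a null IHC result could be read as stronger evidence of no effect than it is.

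**Working it through.** **Inputs from the plan.** Control changes of -1/0/+1 with 10/80/10%; treated patients 50% unchanged and 50% up one or two steps; significance at 0.05; 50 patients planned (Section IV, Enrollment), which is 25 per arm if allocation is 1:1.

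**Assumed, because the plan is silent.** Two-sided testing; 1:1 allocation; one-step/two-step splits of 50/0, 40/10 or 25/25%; the baseline distributions shown below. Both 20 and 25 per arm are used because the companion power figures disagree: the 0.91 SD t-test figure fits 20 per arm (80.1%; 88.3% at 25), while the Fisher figure fits 25 (80.5% at 0.705 v 0.295; 62.6% at 20).

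**Test.** With n per arm, N = 2n and tie-group sizes t, W is the sum of treated midranks minus n(N+1)/2, and

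Var(W) = (n²/12) × [(N+1) − Σ(t³−t)/(N(N−1))].

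Reject if |W|/√Var(W) > 1.96.

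**Step 1: reproduce the stated 90% with no bound.**

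| Per arm | Split 50/0 | Split 40/10 | Split 25/25 |
|---|---|---|---|
| 20 | 88.9% | 90.5% | 93.1% |
| 25 | 94.9% | between | 97.1% |

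The stated figure reproduces at 20 per arm. At 25 per arm the same model gives 95 to 97%.

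**Step 2: apply the bounds.** Draw a baseline score, add the stated change, and truncate to 0–3 in both arms. The share of treated women who can rise becomes 0.5 × (1 − share at 3+): 0.5 × 0.80 = 40% with 20% at 3+, 0.5 × 0.75 = 37.5% with 25%, and 0.5 × 0.60 = 30% with 40%.

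**Step 3: adjust.** Fit a linear model of post score on arm plus baseline category. Ranges cover the 40/10 and 25/25 splits.

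| Baseline 0/1+/2+/3+ (%) | Per arm | Bounded Wilcoxon on change | Post score adjusted for baseline category |
|---|---|---|---|
| 20/30/30/20 | 20 | 79–81% | 80–84% |
| 25/25/25/25 | 20 | 76–78% | 78–81% |
| 10/20/30/40 | 20 | 68–70% | 71% |
| 20/30/30/20 | 25 | 88–90% | 90–92% |
| 25/25/25/25 | 25 | 86–87% | 89–90% |
| 10/20/30/40 | 25 | 78–80% | 82–83% |

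Adjustment raised power in every setting. The separate simulation runs gave gains of 0.5 to 5, 1 to 4 and 2 to 4 points. Entering baseline as a linear term gave 2 to 6. Type I error of the category model was 4.1 to 5.1%. These figures use the model's own t-test; the re-randomization p-value was not simulated.

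The first two baselines are symmetric, so their figures apply equally to Survivin with the sign reversed and the floor in place of the ceiling.

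**Step 4: how much of the loss comes back (25 per arm, 25/25 split).**

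- Uniform baseline: power falls from 97% to 87.4%, and adjustment gives 91.3%. That recovers 3.9 of 9.6 points, about 41%.
- High baseline: power falls from 97% to 80.1%, and adjustment gives 84.7%. That recovers 4.6 of 16.9 points, about 27%.

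**The case against.** A reader might infer that the 90% is overstated and that true power is 70 to 80%. The documents do not support that. Section VI states the distribution of observed change, so the unchanged half may already include capped tumours; truncating again would then count the ceiling twice. The stated changes are also feasible at the harshest baseline above. With 10/20/30/40, 60% can rise and 30% can rise two steps, against the 50% and (under an even split) 25% needed. Power of 70 to 80% arises mainly at 20 per arm, or at 25 per arm only with about 40% at 3+. A harsher variant that truncates only the treated arm gives about 75 to 86% at 25 per arm with 20 to 30% at 3+, again on assumed baselines. This objection stands: the ceiling makes the figure possibly optimistic, not demonstrably wrong.

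The trial's hypothesis also points away from the limiting bounds. If p53 is repressed before treatment, proteins that it activates should start low and Survivin high, each with room to move. That is a fair reason to expect a small loss, but the plan gives no baseline data to confirm it.

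It is tempting to say that adjustment removes the ceiling problem. It does not; Step 4 shows most of the loss remains. A Wilcoxon test stratified by baseline (van Elteren) stayed within about 3 points of the unadjusted test, with little or no gain.

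A reader might also infer from "The IHC endpoints will be rounded to the nearest 10% by the pathologist" that the analysis discards percentage data on these markers. That sentence does not name the four proteins, and Section V says they are scored qualitatively for intensity. Nothing can be built on it.

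Finally, the planned test is valid, this is a pilot, and the list of adjustment factors is open-ended. All true. But those adjusted analyses are exploratory, and baseline score is the most directly relevant covariate left unnamed. A linear model does assume equally spaced steps, which is a real limitation.

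**Conclusion.** The point holds as a modest improvement in efficiency. The Wilcoxon comparison of changes is a valid randomised comparison that makes little use of a baseline score already being collected. Adjusting the post score for baseline category gains about 1 to 5 points of power under assumed baselines, with type I error near 5%.

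The power statement is incomplete rather than shown to be wrong. About 90% corresponds to 20 per arm with no bound. If the stated changes make no allowance for capped tumours and 20 to 25% of women start at 3+, power is about 76 to 81% at 20 per arm or 86 to 90% at 25. All of this rests on the assumed baseline distributions, the one-step/two-step split, 1:1 allocation and two-sided testing.

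**What to change.** In Section VI, make the main IHC comparison for each protein a linear model of the post-treatment score on arm plus baseline score category. Take the p-value by re-randomization following the actual blocked allocation. Keep the change-score Wilcoxon as a sensitivity analysis; it covers the equal-spacing assumption. A plain proportional-odds likelihood-ratio test is less attractive here, since it gave about 7% type I error at 25 per arm.

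Rerun the power simulation with scores bounded at 0 and 3+. State n per arm, the one-step/two-step split, the assumed baseline distribution and whether the stated changes already allow for capped tumours. Give Survivin its own scenario, with a fall and a floor at 0.

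The cost is a revised paragraph and a few lines of code, with no new tissue, visits or patients. The restated power may be less favourable than 90%.

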Patients eligible for this study must have histological diagnosis of invasive breast cancer. The tumor must be ER α positive as defined by having an Allred score 3 or greater for ER α on a core biopsy by immunohistochemistry (IHC). IHC for p53 will be done on the core biopsy specimen, but will not be used as an eligibility criterion. The paraffin block (or 15-5 microns tissue thickness on charged slides) used for ER determination will be recut for p53 immunohistochemical staining using a commercially available antibody detection system (Dako Corporation, Carpinteria, CA) according to the manufacturer's protocol. The results of the p53 status by IHC will not be used for eligibility. The p53 status will be confirmed in resected tumor tissue by high resolution sequence analysis strategy (see under required studies). Inclusion and exclusion criteria for this study are shown above. Only those disease response assessments required for standard of care management will be undertaken. There will be no intervention for patients who are randomized to arm 1. Patients randomized to arm 2 will receive tamoxifen 20 mg by mouth daily for 28 days immediately preceding standard surgical therapy and 5000 units of subcutaneous heparin on day 29 in the holding area on day of surgery.

Women who agree to participate in this study will undergo a complete history and physical examination as part of their clinical care. The history and physical will include questions about prior history of thrombosis and stroke and complete medication history. Gynecologic history will be obtained as well including LMP, history of dysfunctional bleeding, recent pap smears, and smoking history. History and physical will be done standard of care and the study can use history and physical from 4 weeks prior to consent date for baseline. The patients will undergo standard of care blood work for staging of their breast cancer as per national clinical guidelines.

A Symptom Diary and a pill diary (See appendix 3 &4) will be supplied to the patient by the study coordinator to be maintained by the patient throughout participation in the study if randomized to study drug. Symptom Diary will be used as patient tool only. These will be reviewed by the study coordinator with the patient at the 2 week visit and again on the day of surgery.

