Standard surgical therapy will be offered to the patient based on the size, location of their tumor or presence of multiple tumors. After the completion of the surgical resection, two core biopsies of the surrounding normal breast tissue will be taken. One will be used to evaluate for tamoxifen and tamoxifen metabolite levels as well as estradiol and estrone levels in the breast tissue. The second will be stored for future pharmacogenomic studies.

Sequential compression devices (SCD's) will be used as part of standard of care for all women undergoing general anesthesia. Even though there is no data to suggest that a short intervention with tamoxifen will increase the risk of thrombosis, only women who get the tamoxifen arm will receive 5000u of subcutaneous heparin in the pre-operative holding area in addition to the use of SCD's for added prophylaxis.

Patients will undergo adjuvant therapy according to the findings of their surgical pathology. If the patient undergoes Oncotype testing as part of their standard of care, we will collect that information as part of our clinical data for analysis.

ENROLLMENT: Patients would be enrolled in this study at both the University of Chicago and the multidisciplinary breast clinic at RPCI. We plan to accrue 50 patients to this study over 9-year study duration. Anticipated rate of accrual would be 2-3 patients a month.

Tamoxifen is commercially available as a 20 mg tablet. The appropriate grant supporting the study will pay for the tamoxifen and will be provided free-of-charge to patients enrolled in this study.

V. REQUIRED STUDIES

Collaborating institutional staff pathologist will supervise all pathology examinations.

Estrogen Receptor, Progesterone Receptor And Her2 Expression Status:

Biopsy specimens: Estrogen and progesterone receptors are critical for inclusion in this protocol and should either be available as a part of routine analysis or will be done as a part of screening for this study in patients otherwise eligible for the study. Enrollment in the study will be predicated on the presence of ER based on an Allred score of 3 or above. The results of the p53 status will not be used for eligibility and will be determined at the end of study. HER2 expression status is not required prior to accrual.

Genotyping:

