3. PATIENT REGISTRATION AND RANDOMIZATION ASSIGNMENT

Phase II protocol registration instructions:

The **Subject Enrollment Log** must be faxed to the CRS Network Office within 24 hours of the date the patient is consented. Once the Principal Investigator has determined that eligibility has been met, complete the **Patient Registration Form** and **fax it** to the RPCI Network Office at [contact].

Note: The patient completes the **Gender, Race, and Ethnicity form** and this is placed in the study binder.

Roswell Park Cancer Institute does not grant exceptions to eligibility criteria.

Randomization Assignment:

Patients will be allocated to treatment or control by block randomization (block size=4). The randomization assignment list will be maintained at RPCI. The nurse/coordinator from University of Chicago will notify the RPCI Network office for a randomization assignment by sending the completed patient registration form to [contact]. The Network Monitor **or designee** will randomize the patient and send the randomization assignment to the nurse/coordinator at University of Chicago.

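### One fixed block size of 4, printed in site-facing text of an unmasked trial, leaves up to a third of assignments certain to anyone who sees them all in order

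*Combined protocol and SAP*

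**What the plan says.** Section VI (Randomization) and Appendix 2, section 3, the registration instructions for network sites, carry the same sentence: "Patients will be allocated to treatment or control by block randomization (block size=4". Neither place mentions varied sizes, stratification by site, an allocation ratio, or withholding the size from sites.

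- **Custody of the list.** "The randomization assignment list will be maintained at RPCI". RPCI also recruits: "Patients would be enrolled in this study at both the University of Chicago and the multidisciplinary breast clinic at RPCI".
- **Release.** For University of Chicago patients, the coordinator sends in a completed registration form. The Network Monitor or a designee then randomizes and is to "send the randomization assignment to the nurse/coordinator at University of Chicago". The documents do not describe how RPCI's own patients are randomized, or who at RPCI is kept from the list.
- **Masking.** Section IV: "There will be no intervention for patients who are randomized to arm 1". The other arm takes tamoxifen daily without a placebo. The documents do not use the term open-label, but the trial is open in effect. The only treatment masking described is for IHC, "with all pathology personnel blinded to treatment assignment" (section V).
- **Size.** "We plan to accrue 50 patients to this study over 9-year study duration" (section IV, Enrollment).

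**The concern.** With a known block of 4, the last assignment in each block can be deduced, and sometimes the third as well. Someone who can deduce the next assignment can decide whether or when to register a particular patient. That is selection at entry, and masking whoever reads the assay afterwards does not prevent it.

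Two features of the plan make this relevant here. Section VI itself says that the responses may be related to age, smoking and menstrual-cycle position, all of which staff can know before registration. Section V explains that before-and-after comparison is not feasible for ChIP and qRT-PCR, because the diagnostic biopsy yields too little tissue, and PLA is planned on arrays made from excised tumor. The ChIP/PLA and mRNA comparisons are therefore between groups at surgery only, with no baseline measurement to correct an imbalance. Covariate adjustment is planned only as an exploratory analysis.

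**Working it through.** The plan gives no predictability figure, so there is none to reproduce.

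**1. Allocation ratio (assumed 1:1).** The Fisher statement in section VI, "which has 80% power to detect a difference of about 0.41 between the two group", can be checked at 25 per arm. Exact two-sided power is 0.782 for 0.70 against 0.30, and 0.805 for 0.705 against 0.295 (a difference of 0.41). The stated 80% is therefore consistent with 50 patients split equally. This supports 1:1 but does not prove it.

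**2. Observer who sees every assignment in order.** A block with two places per arm has 6 equally likely orderings. An assignment is certain once one arm has used both its places.

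| Position in block | P(certain) | P(best guess correct) |
|---|---|---|
| 1 | 0 | 1/2 |
| 2 | 0 | 2/3 |
| 3 | 1/3 | 2/3 |
| 4 | 1 | 1 |
| Mean | (4/3)/4 = 1/3 | (17/6)/4 = 0.708 |

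Fifty patients make 12 full blocks plus 2 patients:
- Certain: 12 × 4/3 + 0 = 16 of 50 (32%).
- Correct best guesses: 12 × 17/6 + 1/2 + 2/3 = 35.2 of 50 (70.3%), against 50% with no information.

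If the ratio were 3:1, the certain fraction in full blocks would be (0 + 1/4 + 1/2 + 1)/4 = 43.8%.

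**3. A site that sees only its own assignments on one shared list.** Let q be the site's share of enrolment. Suppose each patient independently comes from that site with probability q, and that the site knows the overall patient count. It needs at least two of its own earlier assignments in the block.
- Position 3: q² × 1/3.
- Position 4: q³ (all three earlier assignments seen) + 3q²(1 − q) × 1/3 (exactly two seen, and in the same arm) = q².
- Mean over the four positions: (q²/3 + q²)/4 = q²/3.

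This gives 0.09/3 = 3% at q = 0.3, 0.25/3 = 8% at q = 0.5, and 0.49/3 = 16% at q = 0.7. If each site has its own list, q = 1 and the full third applies at each.

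**4. Randomly varied block sizes.** Simulated for 50 patients, with sizes drawn at equal probability and an observer who knows the set of sizes and all past assignments:

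| Sizes | Certain | Best guess correct |
|---|---|---|
| 4 only | 32.0% | 70.3% |
| 2, 4, 6 | 4.1% | 70.0% |
| 4, 6 | 5.7% | 69.0% |
| 4, 6, 8 | 2.2% | 67.7% |

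**The case against.** The strongest reply is that the plan already has the main safeguard. University of Chicago assignments are released centrally, after eligibility is settled and a registration form is submitted. The enrollment log is due within 24 hours of consent, and eligibility exceptions are not granted. IHC is read masked and analyzed as a within-patient change. This is a 50-patient mechanistic pilot, and section VI expects a larger trial to confirm its findings. A fixed block of 4 contradicts nothing in the documents and keeps small arms balanced. Varying the sizes also barely reduces best-guess accuracy, and a good guess may be enough for someone who wants to steer.

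Much of this stands, and it is why the point is minor. Central release and the log narrow the room to act, but they do not stop someone who can predict the next assignment from choosing whether or when to approach or register a patient. Masked IHC reading and change scores protect the IHC endpoint, not the ChIP/PLA or mRNA comparisons. The remark about best guesses is correct: the gain from varied sizes is the loss of certainty and the withholding of the sizes, not unpredictability in general.

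A reader might go further and infer that RPCI recruiters can consult the list. The documents do not say so. They place the list at RPCI and are silent on access, so that is a gap in description and not a documented breach.

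**Conclusion.** The point holds as a minor weakness in allocation concealment. For someone who sees all assignments in order, one third are certain in full blocks (16 of 50, 32%) and about 70% can be guessed. These figures assume 1:1 allocation and knowledge of the printed block size.

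A reader might infer that every site can foresee a third of its own assignments. The documents do not support that. They describe one list and no stratification by site, which gives about 3% to 16% at enrolment shares of 30% to 70%, and then only if the site knows the overall count, which no passage says it is told. The full third would apply at each site only if lists were separate.

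Nor do the documents show that enrolment was steered or that any comparison is biased. The size of any resulting bias cannot be estimated from them.

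**What to change.** In both section VI (Randomization) and Appendix 2, section 3, replace the bracketed block size with a statement that block sizes vary at random. Apply this to patients not yet randomized. Have the remaining list generated by a statistician not involved in enrolment, and keep the sizes only in a restricted randomization file. The same edit can state the allocation ratio, whether there is one list or one per site, how RPCI's own patients are randomized, and who at RPCI has no access to the list.

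The cost is one regenerated list and two short wording changes. The statistical price is slightly looser balance. On one list, the final difference between arms is at most half the largest block in use: 2 patients now, 3 if the largest block is 6, and 4 if it is 8.
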